## **6.3 Statistical Methods**

Formal inference and estimation of treatment effects will use a Student's t-test. The mean change (baseline-follow-up) in our outcome variables (inflammatory markers, motivation, step count) in the control group will be compared to the mean change (baseline-follow-up) of the intervention group overtime. A p-value less than 0.05 will be used to determine statistical significance.

The relationship between inflammatory markers, motivation, and engagement in physical activity will be assessed. Given that consistent evidence in populations (including older adults) have shown that supplementation with berries (a source of fiber and anthocyanins) successfully reduces inflammatory markers, we are confident our intervention will successfully lower inflammatory markers. Thus, we will evaluate the relationship between of change in inflammatory markers with change of physical activity utilizing a linear regression.

To determine if change in motivation is on the pathway between change in inflammation and engagement in physical activity, we will use linear regression with and without the addition of change in motivation to the model. If adjusting for change in motivation changes the estimate by >10%, then motivation will be considered a part of the causal pathway. A p-value less than 0.05 will be used to determine statistical significance.

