## 4.2 Recruitment Timeline

Our trial proposes to enroll 40 persons over approximately 6-months. We will recruit for two waves of our intervention. For the first wave of the intervention, we aim to recruit 16 individuals over ~3 months. The 16 individuals will then be randomized to the intervention or control group, and participate in the study for 3 months. During the 3 months the first wave of participants are on the study intervention, we will be recruiting for the second wave (n=24) of the intervention. Once the second cohort of 24 individuals is recruited, they will begin the study intervention as soon as possible. To stay on target, we need to recruit ~7 participants/month. Thus, based on our known research participation rates, and the expected prevalence of depressive symptoms in older adults, we will readily be able to meet our recruitment goal of 40 participants.

There will be two waves of the intervention (n=16 for the first wave, and n=24 for the second wave). For each wave, half of the participants will be randomized to the intervention group and the other half will be in the control group. In an attempt to account for the impact of seasonal variation on physical activity levels, we will employ block (blocks of 4) randomization. For every block of 4 participants, 2 will be randomized to consume the placebo powder and the remaining 2 will be randomized to the blueberry powder.

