Objective Measure of Sedentary Behavior will be measured as a final assessment of eligibility. All participants that pass the in-person screen up to this point will be provided an accelerometer (ActiGraph, GT9X Link), which is a research-grade activity tracker that monitors several aspects of activity, including step counts. They will be instructed to wear the device during the week to use as an objective assessment of their sedentary behavior, specifically their usual daily step count. After a week of wearing the activity monitor, the participant’s ActiGraph will be synched in order to calculate their median daily step count over the past week. Individuals that have a median step count >7,500 steps per day will be excluded. All eligible participants will be asked to continue to wear the ActiGraph for the remainder of the study.

To ensure participants have a stable level of dietary influence on inflammation, all participants will be asked to avoid consumption of certain foods (e.g., fiber-rich and anthocyanin-rich foods; i.e., washout period). Additionally, the week before baseline participants will be asked to fill a 3-day diet record to estimate nutrient intake.

**Baseline Visit (~60 minutes):** At the baseline visit, participants will be asked to turn in their 3-day diet records and sync their ActiGraph devices to transfer their activity data and evaluate engagement in physical activity. Height, weight, vitals, suicidal ideation (P4SS), depressive level (PHQ-9), social network, motivation, and relevant symptoms will be evaluated. Additionally, up to 10 mL of blood will be taken to measure inflammation-related markers in serum. Finally, a personalized daily step goal will be calculated for each participant. Utilizing the step count data assessed during the 2-week washout, the 20% increase of his/her median usual daily steps measured will be calculated and be defined as a personalized step-goal. Study staff will share this personalized step goal with the participant and say, “this is the recommended number of steps you should try to meet each day during the study.” Participants will be given their allotment of powder to consume.

**Social Network:** Subjective perception of social support and connectedness will be evaluated using a validated questionnaire.

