## CHAPTER 6. STATISTICAL DESIGN

## **6.1 Statistical Analysis**

All analyses will be performed by intent to treat, and further evaluated per protocol. As a first step, we will assess distribution characteristics of the primary and secondary outcomes. Where appropriate, transformation of variables to combat skew or other irregularities will be employed. Participant characteristics will be summarized using means, medians, standard deviations, interquartile regions and ranges for continuous variables and sample counts and proportions generated for discrete characteristics. Comparability of treatment arms will be assessed on potentially confounding characteristics using tabular and graphical methods.

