## **6.4 Statistical Power**

The sample size for our pilot study has been chosen to provide a practical basis for developing variance measures of motivation and engagement in physical activity that will be needed to design a subsequent larger randomized controlled trial. The daily step count was the outcome that this study power calculation was based off of. Since studies have not yet evaluated change in step count in response to an anti-inflammatory strategy in our specific population (older, sedentary adults with depressive symptoms), the variations of change that are gathered from this study will be used to estimate power for large scale efficacy trials. Regardless, we have estimated the standard deviation of change in steps utilizing the variation of steps in older, sedentary adults without depressive symptoms previously published. Assuming SD of change=1045, 80% power, and an alpha=0.05, a sample size of 18/group is required to detect a change of 1000 steps/day. An increase in 1000 steps per day was associated with a 16% reduced risk in all-cause mortality. Thus, to account for attrition, we propose a sample size of 20/group. Additionally with a sample size of 20/group, we will also have 73% power (assuming SD of change=41) to detect a change of 30 min/day of sedentary time. Such a change is noteworthy epidemiological evidence suggests that 30 min/day of sedentary time is associated with 17% increased risk of all-cause mortality in sedentary older adults.

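### Section 6.3 compares the arms only by an unadjusted t-test on change; a pre-specified ANCOVA on baseline steps and wave would be a nearly free improvement

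*Combined protocol and SAP*

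**What the plan says.** Section 6.3 names one method for the treatment effect: "Formal inference and estimation of treatment effects will use a Student's t-test". The quantity compared is change from baseline: "The mean change (baseline-follow-up) in our outcome variables (inflammatory markers, motivation, step count) in the control group will be compared to the mean change" in the intervention group, with significance at p below 0.05. The regressions later in 6.3 relate changes in markers, motivation and activity to one another; they do not estimate the arm effect. No other section adjusts the arm comparison for baseline or wave.

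Three other places bear on this:

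- Section 4.2 plans waves of 16 and 24, with blocks of 4 intended to deal with season. It states: "For each wave, half of the participants will be randomized to the intervention group and the other half will be in the control group".
- Section 6.1 says: "Comparability of treatment arms will be assessed on potentially confounding characteristics using tabular and graphical methods". It gives no consequence if the arms differ.
- Section 6.4 sizes the trial on the change score: "Assuming SD of change=1045, 80% power, and an alpha=0.05, a sample size of 18/group is required to detect a change of 1000 steps/day". On the source of that SD it says: "we have estimated the standard deviation of change in steps utilizing the variation of steps in older, sedentary adults without depressive symptoms previously published". It gives no SD at either time point and no correlation between them.

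**The concern.** A change score subtracts the whole baseline value. That is ANCOVA with the baseline slope fixed at 1. When the true slope is below 1, subtraction overcorrects, leaves avoidable noise in the comparison, and lets a chance baseline difference between two groups of 20 move the estimate. Fitting the slope removes this.

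Wave raises a similar point. The randomisation is balanced by wave because activity may vary with season, but the analysis then leaves wave out, so any wave difference in change stays in the error term.

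The third issue is timing. The arms will be compared on possible confounders, and nothing says what happens if they differ. An adjustment adopted after that look would be post hoc. What is at stake is precision from 40 people and a clear rule set in advance, not the validity of the planned test.

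**Working it through.** **Inputs from section 6.4:** SD of change 1045, difference 1000 steps/day, alpha 0.05, power 80%, 18 per group required, 20 per group proposed. Section 6.2 sets 80% retention as the feasibility criterion; 16 per group is that rate applied equally to both arms.

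**Assumed, because the documents do not give them:** rho, the baseline to Week 12 correlation of median steps, and k, the Week 12 SD divided by the baseline SD.

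**Step 1, the plan's own figure.** n = 2 × (1045 × 2.802 / 1000)² = 17.1, rounded up to 18 per group. This reproduces the stated size with a two-sided test. By the noncentral t with 2n − 2 degrees of freedom, the planned test has 83.9%, 79.6% and 74.5% power at 20, 18 and 16 per group.

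**Step 2, residual SD under ANCOVA.** Hold the SD of change at 1045:

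- baseline SD: s0 = 1045 / √(1 + k² − 2·rho·k)
- ANCOVA residual SD = k · s0 · √(1 − rho²)

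For example, k = 1 and rho = 0.5 give s0 = 1045 and residual SD = 1045 × √0.75 = 905.

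**Step 3, power with baseline and wave in the model.** Degrees of freedom are 2n − 4, and the variance is multiplied by 1 + 1/(2n − 5) for estimating the slope. At 20 per group, against 83.9% for the t-test:

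| k | rho 0.5 | rho 0.7 | rho 0.8 | rho 0.9 |
|---|---|---|---|---|
| 1.0 | 91.8% | 88.3% | 86.4% | 84.6% |
| 1.1 | 89.4% | 85.7% | 83.9% | 82.7% |
| 1.2 | 87.5% | 84.0% | 82.8% | 83.6% |

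The range is −1.1 to +7.9 points. At 16 per group, against 74.5%, the values are 84.2 / 79.5 / 77.2 / 74.9% for k = 1.0 and 78.5 / 74.2 / 72.9 / 73.7% for k = 1.2.

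**Step 4, worst case for any rho and k.** Residual variance is largest relative to the variance of change when the slope rho·k equals 1; the residual SD is then 1045. Power is 82.7%, 78.2% and 72.8% at 20, 18 and 16 per group, which is 1.1, 1.4 and 1.7 points below the t-test.

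**Step 5, precision.** The 95% confidence interval half-width at 20 per group is 669 steps as planned. For rho 0.5 / 0.7 / 0.8, ANCOVA gives 589 / 627 / 645 at k = 1.0 and 634 / 668 / 679 at k = 1.2. The worst case is 680.

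**Step 6, baseline imbalance.** A one-standard-error chance difference in baseline moves the change-score estimate by (1 − rho·k) · s0 · √(2/20). For rho 0.5 / 0.7 / 0.8 that is about 165 / 128 / 105 steps at k = 1.0 and 119 / 61 / 18 at k = 1.2. This is another view of the noise already counted in step 3, not a further gain.

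**Step 7, wave.** In simulation (rho 0.7, k = 1.0), with mean change differing between waves by 0 / 500 / 1000 steps, the t-test had 84.1 / 82.9 / 78.1% power and the change score adjusted for wave had 84.1 / 84.3 / 84.2%. The wave differences are assumed. Including wave costs about 0.1 point at 20 per group.

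**Step 8, validity.** In simulation, the t-test's type I error was 0.049 to 0.052 with no wave effect and 0.041 to 0.046 with a 500-step wave effect on change. ANCOVA gave 0.048 to 0.052 in both cases.

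**Step 9, which part of the table is likely.** Low rho needs a homogeneous sample: at k = 1, rho 0.5 / 0.7 / 0.8 / 0.9 implies a baseline SD of 1045 / 1349 / 1652 / 2337. As an illustration only, baselines spread evenly over 0 to 7,500 have SD 7500/√12 = 2165, so rho = 1 − 1045² / (2 × 2165²) = 0.88. Power is then about 85%, a gain of about 1 point. Two features in section 5.2 could push k above 1: "Individuals that have a median step count >7,500 steps per day will be excluded", which truncates baseline, and the goal tied to each person's own level, "the 20% increase of his/her median usual daily steps measured will be calculated and be defined as a personalized step-goal".

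**The case against.** The strongest objection is that this is a preference. The planned test is unbiased under randomisation, agrees with the sizing in 6.4, and leads to no wrong conclusion. The benefit depends on two quantities the documents do not contain. Six of the twelve cells in the table gain less than 1 point, and the features in section 5.2 point towards the less favourable rows. In a pilot meant mainly to estimate variances, a few points of power matter little. Wave is already balanced by design, section 6.2 already plans interval estimates of the variation in change, and nothing says the comparability tables will be used to choose covariates.

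Much of this stands. The test is valid, the power gain may be negligible, and adjusting for wave helps only if change differs by wave. The range of −1 to +8 belongs to the stated grid; outside it, for instance at rho 0.3 with k = 1, the gain is larger (about 11 points).

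It does not remove the case for the change. Steps are the primary outcome and are tested at p below 0.05, so precision counts. The cost is bounded whatever rho and k turn out to be, while the possible gain is several times larger. SDs of change alone will not tell the later trial what an adjusted analysis would need. Closing the question of imbalance in advance is worthwhile even with no power gain. Section 6.4 can keep its sample size, since its power figure would be overstated by at most about 1 point at 20 per group.

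**Conclusion.** The point holds as an improvement that should be made; the plan contains no error here. Section 6.3 estimates the treatment effect without conditioning on baseline or wave. At 20 per group, adjusting for both changes power by −1.1 to +7.9 points, given the plan's SD of change and difference, a two-sided 0.05 test, rho from 0.5 to 0.9, and k from 1.0 to 1.2. Gains near the top need a homogeneous sample with similar SDs at both times. If Week 12 steps are more spread than baseline steps, the gain shrinks or vanishes.

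The recommendation rests on the small, known downside and on settling the handling of imbalance beforehand. It should not be presented as a remedy for dropout. Falling from 20 to 16 per group costs 83.9 − 74.5 = 9.4 points. ANCOVA at 16 per group recovers all of that only at rho 0.5 with k = 1.0, and none of it at rho 0.7 or 0.8 with k = 1.2.

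**What to change.** Before unblinding:

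- In 6.3, name as primary an ANCOVA of Week 12 median daily steps on arm, baseline median steps and wave. Using change as the outcome with the same covariates gives the same arm estimate.
- Use the same form for sedentary minutes, motivation and the inflammatory markers, with baseline on the same transformed scale as the outcome.
- Keep the t-test on change as a sensitivity analysis.
- In 6.1, state that the comparability tables will not be used to select covariates.
- In 6.4, note that the sample size was derived for the change-score t-test.
- Report the observed baseline to Week 12 correlation and both SDs, for planning the later trial.

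The cost is SAP wording, two degrees of freedom, and at most 1.1 points of power at 20 per group (1.4 at 18, 1.7 at 16). No new data are needed.

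### Section 6.3 specifies no randomised-arm term in the regressions of step change on marker change, so the slope is confounded by arm if any of the step effect bypasses the marker

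*Combined protocol and SAP*

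**What the plan says.** Section 6.3 (Statistical Methods) has two parts. The first compares mean change between control and intervention by t-test and names both groups. The second concerns mechanism: "we will evaluate the relationship between of change in inflammatory markers with change of physical activity utilizing a linear regression". For the role of motivation, "we will use linear regression with and without the addition of change in motivation to the model", and motivation is placed on the causal pathway if the estimate moves by more than 10%. For these regressions too, "A p-value less than 0.05 will be used to determine statistical significance".

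The only predictors named are change in marker and change in motivation. Neither 6.3 nor 6.1 and 6.2 supplies an arm covariate, a stratified model or a within-arm slope.

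Two other statements matter here. Section 6.3 says "we are confident our intervention will successfully lower inflammatory markers". Section 6.4 says "Assuming SD of change=1045, 80% power, and an alpha=0.05, a sample size of 18/group is required to detect a change of 1000 steps/day". The working hypotheses are thus that the powder moves both the predictor and the outcome of this regression.

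**The concern.** The question is whether people whose inflammation falls more also increase their activity more. A slope fitted to all participants without arm mixes two sources of association: the link between people within an arm, and the line joining the two arm means. If the powder lowers the marker and, by another route, raises steps, the arm means alone produce a negative slope, even when marker and steps are unrelated within each arm. The regression then cannot tell a link between inflammation and activity from a powder that shifted both, and the t-tests already address whether it shifted each.

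At stake is the mechanistic reading of the pilot. Aim 3 makes mediation by motivation an explicit hypothesis, and the results are meant to inform a larger trial.

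**Working it through.** **Inputs.**
- Step effect 1000/day, SD of change 1045 (6.4): ds = 1000/1045 = 0.957 SD.
- Group size 20 per arm (6.4: "to account for attrition, we propose a sample size of 20/group"), with 18 per arm as the planned number after attrition. Allocation is 1:1 (4.2: "2 will be randomized to consume the placebo powder and the remaining 2 will be randomized to the blueberry powder").
- Alpha 0.05 (6.3). Sidedness is not stated; two-sided is assumed.
- Marker effect dm, in SDs of marker change: **an assumption**. The documents give its direction only, so it is ranged from 0.2 to 1.2 SD.

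**The plan's own figure.** n per group = 2 × (1.960 + 0.842)² × (1045/1000)² = 2 × 7.85 × 1.092 = 17.1, rounded up to 18. This reproduces the stated 18 per group with a two-sided test. (The noncentral t gives 79.6% power at 18 and 83.9% at 20.)

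**Model with no true link.** Marker change M = −dm × arm + e1; step change Y = ds × arm + e2; e1 and e2 are independent standard normals. Within an arm the true slope is zero. With N participants in total, the slope of Y on M without arm is approximately

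−(N × dm × ds / 4) / [(N − 1) + N × dm² / 4].

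For N = 40 and dm = 0.8: −(40 × 0.8 × 0.957 / 4) / (39 + 6.4) = −7.66 / 45.4 = −0.169. Simulation gives −0.169.

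**Rejection rates, full planned step effect** (200,000 simulated trials per setting):

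| Marker effect (SD) | 20/arm, no arm term | Multiple of 0.05 | 18/arm, no arm term | 20/arm, arm in model |
|---|---|---|---|---|
| 0.2 | 5.8% | 1.2 | 5.7% | 5.0% |
| 0.5 | 9.8% | 2.0 | 9.3% | 5.0% |
| 0.8 | 16.8% | 3.4 | 15.5% | 5.0% |
| 1.0 | 22.6% | 4.5 | 20.9% | 5.0% |
| 1.2 | 28.9% | 5.8 | 26.4% | 5.1% |

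**Smaller step effects, 20/arm.** At half the planned effect (500/1045 = 0.478 SD) the rate without arm is 6.4% to 9.9% for marker effects of 0.5 to 1.0 SD, or 1.3 to 2.0 times nominal. If the powder moves only steps or only the marker, the rate stays at about 5%.

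**Power cost of adjusting.** Here the link is real (Y = b × M + e2) and arm has no direct effect on steps, N = 40:

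| Within-arm slope b | Marker effect (SD) | Without arm | With arm |
|---|---|---|---|
| −0.4 | 0.8 | 73% | 66% |
| −0.3 | 1.0 | 53% | 44% |
| −0.4 | 1.0 | 76% | 66% |
| −0.5 | 1.0 | 91% | 84% |

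Over marker effects of 0.5 to 1.0 SD and slopes of −0.3 to −0.5, the loss is about 3 to 10 points. Power falls because the between-arm spread in the marker no longer counts as evidence.

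**The case against.** The strongest reply is that the plan's conceptual model sends the effect on steps through inflammation and motivation. If the whole effect ran through the marker in the regression, the slope without arm would be unbiased and more powerful. The trial is double-blind, the step goal is given to participants in both arms, and the documents name no route by which the powder would raise steps other than through inflammation. The 1000 steps/day is also a difference used for sizing, and Aim 3 says only that steps tend to rise. This stands as far as size goes: the tabulated rates assume that the full step effect bypasses the marker, which is the extreme case. It does not remove the problem, because full passage through the marker is part of what the analysis is meant to examine. There are also three markers, and an effect carried by one may bypass another.

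Three stronger readings are tempting, and the documents do not support them.
- That the false-positive rate is 3 to 4 times nominal. That multiple needs the full step effect and a marker effect of about 0.8 to 0.95 SD, which appears nowhere in the plan.
- That the plan states that the arms are pooled. It does not; pooling without arm is the natural reading of a model with no arm term and no stratification.
- That the pilot will report a false mechanism, or that its treatment comparison is inflated. The first is a prediction. The second is wrong, since treatment effects are tested by the t-test.

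**Conclusion.** The point holds as a gap in the secondary mechanistic analysis. As written, 6.3 leaves the slope open to confounding by arm whenever the powder changes the marker and also affects steps outside it. Under no within-arm link, normal errors, a two-sided test, the full planned step effect and 20 per arm, the error rate runs from about 6% to 29% for assumed marker effects of 0.2 to 1.2 SD. It is lower with a smaller step effect and nominal if only one variable moves. With arm in the model it is about 5% throughout. The same omission affects the model with motivation added, but how the 10% change-in-estimate rule behaves was not evaluated, so no figure is attached to it.

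**What to change.** In 6.3, state that randomised arm is a covariate in each regression of change in steps on change in a marker, both with and without change in motivation. State that any conclusion that inflammation is linked to activity rests on the arm-adjusted coefficient and its confidence interval, and that the unadjusted slope is reported as descriptive only.

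This takes about two sentences and one degree of freedom, with no new data. The real cost is the power loss of about 3 to 10 points shown above, which applies if the link is genuine and arm has no direct effect on steps.

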## CHAPTER 3: RESEARCH DESIGN

### 3.1 Study Objectives and Aims

The overall objective of this study is to gather preliminary evidence on the feasibility and effectiveness of an intervention supplementing fiber and anthocyanins to usual diet compared to control (placebo). We will conduct a 3-month, double-blind randomized, parallel-arm, pilot study in 40 sedentary, older adults with depressive symptoms that is designed to improve inflammation, motivation, and consequent engagement in physical activity. Our specific aims are:

**Aim 1:** Determine the feasibility of an intervention supplementing usual diet with fiber (8 g/day) and anthocyanins (600 mg/day). We hypothesize at least 80% of the participants enrolled will complete the 3-month intervention.

[figure not shown]
**Aim 2:** Gather preliminary evidence on the impact of fiber and anthocyanin supplementation on relevant inflammatory markers. We hypothesize markers relevant to inflammation (interleukin-6, C-reactive protein, and brain-derived neurotrophic factor) tend to reduce after 3 months of fiber and anthocyanin supplementation compared to control.

**Aim 3:** Obtain preliminary evidence on the efficacy of fiber and anthocyanin supplementation to improve the engagement in physical activity, and further determine if this effect is mediated by change in motivation (via Motives for Physical Activities Measure-Revised questionnaire). We hypothesize the physical activity (i.e., average daily step count via accelerometer) tends to increase after 3 months of fiber and anthocyanin supplementation compared to control, and that a substantial portion of this effect is mediated via an increase in motivation.

Our overall hypothesis is that a 3-month dietary intervention supplementing fiber and anthocyanins in sedentary, older adults with depressive symptoms will be feasible and demonstrate preliminary efficacy.

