### 3.5 Study Endpoints

Primary Outcomes – The primary outcome for this study will be engagement in physical activity.

1. **Engagement in Physical Activity:** Engagement in physical activity will be evaluated by the median # of steps per/day (via ActiGraph) of the previous two weeks before each visit (e.g., 2 weeks before baseline or 2 weeks before follow-up). We will also evaluate median sedentary minutes/day of the previous two weeks before visits.

Secondary Outcomes – We will evaluate several secondary outcomes including:

1. **Feasibility** : Feasibility will be defined as participant retention rate (i.e., number of participants that complete the intervention/total randomized).
2. **Inflammatory Biomarkers:** Serum markers relevant to inflammation, (serum brain-derived neurotrophic factor, BDNF; C-reactive protein, CRP; interleukin-6, IL-6) at baseline and follow-up will be measured by Quest Diagnostics or our collaborators at the University of Connecticut Metabolic Phenotyping Lab.
3. **Motivation:** Motivation to engage in physical activity (our proposed mediator between inflammation and physical inactivity) will be assessed by the self-report questionnaire Motives for Physical Activities Measure-Revised that has been used in middle-aged and older adults.

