## **6.2 Outcome Variables**

Feasibility is defined as participant retention (e.g., the number of participants that complete the intervention out of all participants randomized to an intervention arm), however others will be explored. Feasibility outcomes will be summarized using sample quantities and corresponding 80% confidence interval estimates. The intervention will be considered feasible if at least 80% of the participants randomized, complete the final follow-up.

Relevant inflammatory markers (C-reactive protein, interleukin-6, and brain derived neurotrophic factor) will be measured in blood collected from participants at baseline and final follow-up. Change in inflammatory markers will be calculated. The distribution of change in inflammatory markers will be summarized using sample quantities and kernel density estimates. We will develop 80% confidence interval estimates of inter- and intra-individual variation (i.e., standard deviation) of change in these measures.

Motivation to engage in physical activity will be assessed via self-report questionnaire, Motives for Physical Activities Measure-Revised. Change in motivation will be calculated between baseline and follow-up periods. The distribution of change in motivation scores will be summarized using sample quantities and kernel density estimates. We will develop 80% confidence interval estimates of inter- and intra-individual variation (i.e., standard deviation) of change in these measures.

Engagement in physical activity will be defined as the median daily-step count over 2 weeks prior to each mid-point and/or follow-up visit. We chose the median daily step count, because step counts varies from day to day. Change in median step count will be calculated between the baseline and follow-up. The distribution of change in physical activity will be summarized using sample quantities and kernel density estimates. We will develop 80% confidence interval estimates of inter- and intra-individual variation (i.e., standard deviation) of change in these measures.

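### The 10% change-in-coefficient rule for mediation has no interval, direction or stated significance gate, and no planned analysis estimates the mediated supplementation effect in Aim 3

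*Combined protocol and SAP*

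**What the plan says.** Aim 3 (section 3.1) sets out to estimate the effect of supplementation on physical activity and to "further determine if this effect is mediated by change in motivation". Its hypothesis is that a substantial part of the supplementation effect runs through increased motivation.

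Section 3.5 describes motivation differently, as "our proposed mediator between inflammation and physical inactivity".

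Section 6.3 follows the section 3.5 version. It expects the supplement to lower the markers and on that ground says "we will evaluate the relationship between of change in inflammatory markers with change of physical activity utilizing a linear regression". The mediation step compares two such regressions, one of which adds the mediator: "we will use linear regression with and without the addition of change in motivation to the model". The decision rule is: "If adjusting for change in motivation changes the estimate by >10%, then motivation will be considered a part of the causal pathway". The paragraph closes with "A p-value less than 0.05 will be used to determine statistical significance", without saying which coefficient is tested or whether the test conditions the rule.

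Section 6.2 lists three markers: CRP, IL-6 and BDNF. The 80% intervals there are for feasibility and for standard deviations of change. The arm comparisons in section 6.3 are t-tests on each outcome separately.

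**The concern.** There are two separate problems.

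First, the rule turns a shift in a point estimate into a yes/no causal statement. A coefficient that moves away from zero counts the same as one that attenuates. A slope estimated near zero can change by more than 10% through noise alone. With three markers, the plan does not say which coefficient decides or how three verdicts combine.

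Second, the exposure in the regression is not the exposure in Aim 3. Even a well-behaved rule for inflammation, motivation and steps would not say how much of the supplement's effect on steps passes through motivation.

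At stake is the mediation half of Aim 3. It could be reported as confirmed when there is no mediation, and for a question other than the one the aim poses.

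**Working it through.** **Inputs.** From the plan: 20 per group, so N = 40 (section 6.4); at least 80% expected to complete (Aim 1), so 0.80 × 40 = 32 at the lower end; the 10% threshold and p<0.05 (section 6.3). The plan gives no correlations among changes in inflammation (X), motivation (M) and steps (Y). Those below are assumptions.

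**1. The plan's own figure.** There is no operating figure for the mediation rule. The sample size behind N reproduces: n = 2(1.960 + 0.842)² × (1045/1000)² = 2 × 7.851 × 1.092 = 17.1, rounded up to 18 per group. It concerns the step-count t-test only.

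**2. What the rule measures.** For least squares, b_unadj − b_adj = â × b̂, where â is the slope of M on X and b̂ is the coefficient of M in the model for Y with X. The rule is therefore |â b̂ / b_unadj| > 0.10. With no mediation because a = 0, â still has standard error of about 1/√n in standardised units: 1/√40 = 0.158.

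**3. Hand check.** Take an X–Y slope of 0.3, so the threshold is 0.10 × 0.3 = 0.03, and treat b̂ and b_unadj as fixed.
- M–Y = 0.5: the shift has SD 0.158 × 0.5 = 0.079; 0.03/0.079 = 0.38; P(|Z| > 0.38) ≈ 70%.
- M–Y = 0.3: the shift has SD 0.158 × 0.3 = 0.047; 0.03/0.047 = 0.63; P(|Z| > 0.63) ≈ 53%.

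**4. Simulation.** Trivariate normal change scores, r(X,M) = 0, one marker, n = 40 to 32, 100,000 replicates per cell. Percentage of trials in which the rule is met:

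| Case | r(X,Y), r(M,Y) | As written | Attenuation only | Slope p<0.05 and rule met | Slope p<0.05 and attenuation |
|---|---|---|---|---|---|
| A | 0, 0 | 49-52 | 24-26 | 0.6-0.7 | 0.3 |
| B | 0.3, 0 | 22-29 | 11-14 | about 5 | 2 |
| C | 0.3, 0.3 | 50-53 | 25-27 | 14-16 | 9-10 |
| D | 0.3, 0.5 | 69-72 | 35-38 | 23-27 | 18-20 |

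About half of the as-written positives (47-51%) move away from zero, the opposite of mediation. A favourable case, r(X,Y) = 0.5 with motivation unrelated to both, gives 7-12% as written. If motivation predicts steps (0.3) and the marker is related to neither, the rate is 73-74% as written and about 2% gated.

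**5. Three markers.** If any one marker suffices (an assumption; intercorrelation 0 to 0.5), the as-written rates for A to D are 77-83%, 42-58%, 77-85% and 94-97%. Gated, they are about 2%, 11-13%, 30-39% and 46-62%.

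**6. Comparator.** A 95% percentile-bootstrap interval for the same X–M–Y indirect effect excludes zero in 0.2-0.3%, 0.2-0.3%, 2-3% and about 6% of trials in A to D.

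**7. Aim against analysis.** Aim 3 needs the product of arm → motivation and motivation → steps given arm. The t-test on motivation supplies the first path. No planned model supplies the second, because none contains arm and motivation together. Neither an indirect effect of arm nor a proportion mediated is estimated.

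**The case against.** - **The gate may be intended.** The p<0.05 sentence follows the rule directly, and an identical sentence already closes the t-test paragraph, so it presumably applies to these regressions. Read as a gate on the unadjusted slope, it brings A and B to about 5% or less. This stands for A and B. It does not repair C and D, and the plan does not state it.
- **Case A without a gate is nearly an artefact** of dividing by a slope whose true value is zero. Fair; the case against the rule rests more on C and D. Those are plausible here: section 5.2 gives every participant, in both arms, a personal step goal 20% above usual, so motivation and steps could rise together without inflammation changing.
- **All rates depend on assumed correlations**, the three-marker rates also need an any-one rule that the plan does not state, and the simulation omits arm. All true. The textual gaps do not depend on the simulation.
- **The change of exposure is explained.** Section 6.3 reasons from supplement to markers to steps, consistent with section 3.5, and motivation is compared by arm. The link is therefore incomplete rather than unrelated, but an expectation that the markers will fall does not replace an estimate.
- **Direction is partly given**, since Aim 3 expects motivation to increase. The rule still does not require the coefficient to attenuate.
- **This is a pilot**, mediation is not a listed outcome, and the next trial is to be designed from variance estimates. That limits the consequence and supports an exploratory label; it does not support a causal verdict.

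**Conclusion.** The concern holds. As written, the rule has no stated error rate, and in the four main no-mediation scenarios it is met in 22-72% of trials per marker at n = 40 to 32. It behaves better (7-12%) when inflammation predicts steps strongly and motivation is unrelated to both. On the most generous reading, with a significant slope and attenuation both required, false positives are 2% or less when motivation is unrelated to steps, but 9-20% when motivation independently predicts steps. These figures assume normal change scores, no arm effect and the correlations shown. Two findings rest on the text alone: the rule lacks an interval, a direction, a stated gate and a named marker; and the mediated supplementation effect in Aim 3 is not estimated. The consequence is confined to the mediation part of Aim 3. It should be corrected before analysis.

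**What to change.** Replace the 10% rule in section 6.3 with an estimate of the indirect effect named in Aim 3:

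1. Regress change in motivation on arm (path a). Regress change in steps on change in motivation, adjusting for arm and baseline (path b).
2. Report a × b with a bootstrap confidence interval, resampling within arm, and state the interval level in advance. The rates quoted here are for 95%; section 6.2 uses 80% for other quantities.
3. Claim support only if the interval excludes zero in the hypothesised direction, and label the analysis exploratory.
4. If the inflammation–motivation–steps path is kept, name the marker or say how the three combine. Report its indirect effect with an interval in the same way, and add an arm-adjusted version as a sensitivity analysis.
5. Reconcile the statements of the mediation question in sections 3.1, 3.5 and 6.3.

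Optionally, use week 6 or week 8 motivation, already collected under Table 1, so that the mediator precedes the final two-week step window.

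The cost is SAP wording and a few lines of code, with no new data. The real downside is imprecision. Assuming no direct effect and n = 40 to 32, the interval excludes zero in the hypothesised direction in 15-12% of trials if arm shifts motivation by 0.5 SD and the within-arm motivation–steps correlation is 0.3. This rises to 65-53% at 0.8 SD and 0.5. With no arm effect on motivation it does so in 0.1-3%. A mediation claim becomes less likely, but a wide interval is more useful for planning the larger trial than an unreliable yes/no.
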